9.3.2. PK Endpoints

The PK concentration and parameter populations are defined in [Section 9.2](#).

9.3.2.1. Derivation of PF-07853578 PK Parameters

The plasma PK parameters for PF-07853578, following oral dose administration, will be derived from the plasma concentration-time profiles using standard noncompartmental methods as detailed in [Table 4](#), as data permit. Actual PK sampling times will be used in the derivation of PK parameters. If actual PK sampling times are not available, nominal PK sampling times will be used in the derivation of PK parameters.

Table 4. Plasma PF-07853578 PK Parameters

Parameter	Definition	Method of Determination
AUC _{last}	Area under the plasma concentration-time profile from time 0 to the time of the last quantifiable concentration (C _{last})	Linear/Log trapezoidal method

Table 4. Plasma PF-07853578 PK Parameters

Parameter	Definition	Method of Determination
AUC _{inf} *	Area under the plasma concentration-time profile from time 0 extrapolated to infinite time	AUC _{last} + (C _{last} */k _{el}), where C _{last} * is the predicted plasma concentration at the last quantifiable timepoint estimated from the log-linear regression analysis
C _{max}	Maximum plasma concentration	Observed directly from data
T _{max}	Time for C _{max}	Observed directly from data as time of first occurrence
t _{1/2} *	Terminal elimination half-life	Log(2)/k _{el} , where k _{el} is the terminal phase rate constant calculated by a linear regression of the log-linear concentration-time curve. Only those data points judged to describe the terminal log-linear decline will be used in the regression.
CL/F*	Apparent clearance	Dose/AUC _{inf}
V _d /F*	Apparent volume of distribution	Dose/(AUC _{inf} *k _{el})
AUC _{last(dn)}	Dose-normalized AUC _{last}	AUC _{last} /Dose
AUC _{inf(dn)} *	Dose-normalized AUC _{inf}	AUC _{inf} /Dose
C _{max(dn)}	Dose-normalized C _{max}	C _{max} /Dose

*As data permits.

9.3.2.2. Statistical Methods for PK Data

Plasma concentrations of PF-07853578 will be listed and summarized descriptively by dose (and fasting condition and formulation, if appropriate) and nominal PK sampling time. Individual participant and median profiles of the plasma concentration-time data will be plotted by dose (and fasting condition and formulation, if appropriate) using actual (for individual) and nominal (for median) times respectively. Median profiles will be presented on both linear and log scales.

The plasma PK parameters will be summarized descriptively by dose (and fasting condition and formulation, if appropriate) as applicable. Dose-normalized AUC_{inf}, AUC_{last}, and C_{max} will be plotted against dose (and fasting condition and formulation, if appropriate) using box-and-whisker plots, and will include individual participant values and the geometric means for each dose. These plots will be used to understand the relationship between the PK parameters and dose (and fasting condition and formulation, if appropriate).

If the food effect is assessed, a mixed effects ANOVA will be performed separately on the natural log transformed AUC_{inf}, AUC_{last}, and C_{max} (dose-normalized prior to analysis, if appropriate) with fasting condition included as a fixed effect and participant as a random effect. Further details of this analysis will be provided in the SAP.

If the IDS oral solution is assessed, a mixed effects ANOVA will be performed separately on the natural log transformed AUC_{inf}, AUC_{last}, and C_{max} (dose-normalized prior to analysis, if

appropriate) with formulation included as a fixed effect and participant as a random effect. Further details of this analysis will be provided in the SAP.

Additional PK analyses may be performed if deemed appropriate and may not be included in the CSR.

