An interleaving design will be employed in this study to spread PF-07853578 dose levels across a wide range within an individual participant and to reduce the risk of carryover effects on PK and the anticipated dynamics of PNPLA3 levels return to baseline across the planned dose/exposure range. The duration of time between the interleaving dose escalation periods in Cohort 1 and Cohort 2 will be determined by the time required for analysis and review of the safety, tolerability, and PK data from each dosing period before making a decision on the subsequent PF-07853578 dose level to be evaluated. Therefore, the duration of time between doses in an individual participant will be ≥ 10 days because at high doses of PF-07853578, PNPLA3 levels are predicted to return to baseline in ≤ 7 days.

Based on the predicted $t_{1/2}$ of PF-07853578, plasma concentrations of PF-07853578 are expected to be below the limit of detection in approximately 3 days, thus PK samples are planned to be collected over 72 hours post-dose. However, sampling times, duration of sampling, and/or the length of the interval between doses may be modified and/or extended based on emerging PK. The planned doses in the dose escalation sequence ([Table 3](#)) may be modified or repeated, as guided by emerging safety, tolerability, and PK data but will follow the dose-escalation rules defined in [Section 6.6.1](#).

Neurological examinations will be conducted **CCI**

[REDACTED] . Neurologic signs

will be monitored closely pre- and post-dose, and participants will remain in a closely monitored environment for 72 hours post-dose, which is deemed sufficient based on the predicted effective $t_{1/2}$ of PF-07853578.

Respiratory rate will be assessed CCI

A fasting lipid panel, consisting of total cholesterol, triglycerides, HDL, and direct LDL, will be monitored with clinical safety lab tests CCI

Food may increase PF-07853578 exposures, therefore an exploratory assessment of the effect of food on PF-07853578 PK may be conducted to confirm *in silico* predictions.

CCI

PGx blood samples will be collected for retrospective genotyping of PNPLA3 polymorphism (rs738409) in each participant. This data may enable assessments of differential safety, tolerability, and PK by genotype and may inform the design of subsequent clinical studies with PF-07853578. The results of such analyses are not planned to be included in the CSR.

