3.3. Other Endpoint(s)

3.3.1. Additional Plasma PF-07853578 PK Parameters

Additional plasma PF-07853578 PK parameters, as described in Table 3, will be determined:

Table 3. Additional PF-07853578 Plasma PK Parameters

Parameter	Analysis Scale	PF-07853578
AUC _{inf} (dn)*	ln	D
AUC _{last} (dn)	ln	D
$C_{max}(dn)$	ln	D
CL/F*	ln	D
V _z /F*	ln	D

^{*=}if data permits. Abbreviations: D=displayed with descriptive statistics as outlined in Table 5 in Section 6.3.1; dn = normalized to a 1 mg PF-07853578 dose; ln=natural-log transformed; R = raw (untransformed).

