5.2.3. Mixed Effect Model

A mixed effects model with treatment as a fixed effect and participant as a random effect will be used for analysis of the:

- Effect of food on PF-07853578 PK
- PF-07853578 PK of IDS oral solution relative to the oral suspension formulation.

Estimates of the adjusted (least squares) mean differences (Test-reference) and corresponding 90% confidence intervals will be obtained from the model. The adjusted mean differences and 90% confidence intervals for the differences will be exponentiated to provide estimates of the ratio of adjusted geometric means (Test/Reference) and 90% confidence intervals for the ratios.

The mixed effects model will be implemented using SAS Proc Mixed, with REML estimation method and the Kenward-Roger degrees of freedom algorithm.

Residuals from the models will be examined for normality and the presence of outliers via visual inspection of plots of residuals vs predicted values and normal probability plots of residuals, but these will not be included in the clinical study report. If there are major

deviations from normality or outliers (where studentized [conditional] residuals are greater than 3 or less than -3), then the effect of these on the conclusions may be investigated through alternative transformations and/or analyses excluding outliers. Justification for any alternative to the planned analysis will be given in the report of the study if applicable.

Example code is shown in Appendix 1.

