6.2. Secondary Endpoints

Plasma PK parameters for PF-07853578, as described in Section 3.2, will be listed and summarized descriptively for participants in the PK Parameter Set (as defined in Section 4). Missing values will be handled as detailed in Section 5.3. Each PK parameter will be summarized by dose (and formulation and fasting condition, if appropriate) as applicable.

Table 4. Summary Statistics for PF-07853578 Plasma PK Parameters

Parameter	Summary Statistics	
AUC _{last} , AUC _{inf} *, and C _{max}	N, arithmetic mean, median, cv%, standard deviation,	
	minimum, maximum, geometric mean and geometric	
	cv%.	
T _{max}	N, median, minimum, maximum.	

t _{1/2} .*	N, arithmetic mean, standard deviation, median,
	minimum, maximum.

^{*:} if data permit

Supporting data from the estimation of AUC_{inf} will be listed by dose and treatment (if applicable): terminal phase rate constant (kel); goodness of fit statistic from the log-linear regression (r²); the percent of AUC_{inf} based on extrapolation (AUC_{extrap%}); and the first, last, and number of time points used in the estimation of kel. This data may be included in the clinical study report.

The following plots will be presented using the PK Parameter Set (as defined in Section 4):

- Box and whisker plots for dose-normalized PK parameters [AUC_{inf} (dn), AUC_{last} (dn) and C_{max}(dn)] will be presented in logarithmic scale by dose and treatment (if applicable) and overlaid with observed values of individual participants and geometric means. Geometric means will have a different symbol than the individual values. Individual values from different cohorts will also have a different symbol. A footnote will be added to the plots to indicate that geometric means are presented and that data from all cohorts are presented on the plot.

The following will additionally be presented for the plasma concentration data using the PK Concentration Set (as defined in Section 4):

- a listing of all concentrations sorted by participant ID and nominal time post-dose for each dose and treatment (if applicable) separately. The concentration listing will also include the actual times. Deviations from the nominal time will be given in a separate listing.

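### No slope or interval is planned for the dose–exposure relationship; a descriptive mixed-effects power model, with formulation handled, would supply one from data already collected

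*Protocol*

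**What the plan says.** Protocol 9.3.2.2 plans by-dose summaries and box plots of the dose-normalized parameters, showing individual values and geometric means. It gives the plots their purpose: "These plots will be used to understand the relationship between the PK parameters and dose". SAP 6.2 carries this forward ("Box and whisker plots for dose-normalized PK parameters") and adds that "Individual values from different cohorts will also have a different symbol". SAP Table 3 assigns the dose-normalized parameters only the descriptive code ("D=displayed with descriptive statistics as outlined in Table 5 in Section 6.3.1"). SAP Table 5 lists the statistics, including geometric mean and geometric CV.

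The one PK model in the plan is in SAP 5.2.3: "A mixed effects model with treatment as a fixed effect and participant as a random effect will be used for analysis of the" food effect and the comparison of IDS solution with suspension. Only for those two comparisons does the SAP state that "corresponding 90% confidence intervals will be obtained from the model". SAP 2.1 records no change to the protocol's analysis. Protocol 9.3.2.2 leaves an opening: "Additional PK analyses may be performed if deemed appropriate and may not be included in the CSR".

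On design, Protocol 4.2 says the crossover allows PK to be assessed within as well as between participants, and "An interleaving design will be employed in this study to spread PF-07853578 dose levels across a wide range within an individual participant".

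**The concern.** The plan poses a question, how exposure relates to dose, and answers it by eye. Each box holds about 6 values. Nothing in the box plots or in Table 5 connects a participant's value at one dose with the same participant's value at another. If interleaving places neighbouring doses in different cohorts, a difference between adjacent boxes mixes a dose effect with differences between people.

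What is at stake is the final statement on proportionality in the study report and the dose choice in later studies. There is also a smaller use inside the plan. The food and IDS models may dose-normalize the parameters before analysis (Protocol 9.3.2.2, SAP 6.3.2 and 6.3.3). If the doses compared differ, that step assumes proportionality, and no estimate is planned to support it.

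**Working it through.** **No figure to reproduce.** The plan states no precision, power or CV for PK. Its counts agree: 3 × 8 = 24 participants, and 6 active + 2 placebo = 8 per period.

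**Inputs from the documents.** Doses of 1, 3, 10, 30, 75, 150 and 300 mg (Protocol Table 3), a 300-fold range; 6 active per dose (Protocol 4.2 and 9.5); 90% level, borrowed from SAP 5.2.3.

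**Assumptions.** Cohort 1 receives 1, 10, 75 and 300 mg; Cohort 2 receives 3, 30 and 150 mg; one placebo period per participant over four periods. That gives 7 × 6 = 42 active profiles in 16 participants. Between-participant CV 30–70%, within-participant CV 20–50%.

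**Formulas.** On the ln scale, σ = √ln(1 + CV²).

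- Neighbouring doses, 6 versus 6 different people: half-width = t(0.95, 10 df) × √[2(σb² + σw²)/6]. At CVs of 40%/25%: σb² = ln 1.16 = 0.1484 and σw² = ln 1.0625 = 0.0606, so 1.812 × √0.0697 = 0.478, a factor of ×/÷ e^0.478 = 1.61.
- Power model: ln(parameter) = a + participant + b·ln(dose). The GLS standard error of b at 40%/25% is 0.0208. With 42 − 16 − 1 = 25 df, the half-width is 1.708 × 0.0208 = 0.0355. The matching factor over an R-fold range is R^0.0355: 1.09 for 10-fold and 1.22 for 300-fold.

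| Between/within CV | Neighbouring doses | Slope, no formulation term | Factor over 10-fold | Factor over 300-fold |
|---|---|---|---|---|
| 30%/20% | ×/÷1.45 | ±0.029 | 1.07 | 1.18 |
| 40%/25% | ×/÷1.61 | ±0.0355 | 1.09 | 1.22 |
| 50%/30% | ×/÷1.79 | ±0.042 | 1.10 | 1.27 |
| 70%/50% | ×/÷2.28 | ±0.068 | 1.17 | 1.47 |

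REML simulation (400 runs at each of 30%/20%, 50%/30% and 70%/50%) gave 89–90% coverage. Letting slopes vary between participants (SD 0.05) widens the range over the CVs examined to ±0.038 to ±0.074.

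**Formulation.** Protocol 6.1 lists a low-strength solution, suspensions and a further solution, with the conditions for each redacted. SAP 5.2 treats each formulation as a separate treatment. Suppose solution gives way to suspension after 1, 3 or 10 mg, with an assumed relative bioavailability of 0.7. Without a formulation term, a truly proportional drug has an expected slope of about 0.96, 0.93 or 0.92. At 40%/25%, an interval of ±0.0355 centred on any of these excludes 1. With the term, bias of this kind is removed but the interval widens:

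- 40%/25%: ±0.049, ±0.066 or ±0.080.
- 50%/30%: ±0.059, ±0.079 or ±0.095.

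The half-width is nearly proportional to σw. At a within-participant CV of 50% it is therefore about 0.472/0.294 = 1.61 times the last row, or about ±0.09 to ±0.15.

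**What the interval can show.** A 0.80–1.25 criterion over 300-fold needs the slope interval inside 1 + ln 0.80/ln 300 = 0.961 to 1 + ln 1.25/ln 300 = 1.039. With a true slope of 1 and no formulation term, the simulated chance is about 48% (30%/20%), 4% (50%/30%) and 0% (70%/50%). A half-width above 0.039 cannot meet the criterion at all, and every formulation-adjusted value listed above exceeds it. By contrast, a true slope of 1.1 means 300^0.1 = 1.77-fold drift. An interval of ±0.080 centred there runs from 1.02 to 1.18 and excludes 1.

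**The case against.** Dose proportionality is not an objective or endpoint. PK is secondary, the dose-normalized parameters are exploratory, no hypothesis is tested, and protocol and SAP agree with each other. A descriptive treatment is a legitimate choice. That stands, and it limits how much weight the point can carry.

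A reader might infer that box plots are the only tool and that within-participant data go unused. The documents do not support that. SAP Table 5 gives geometric means and CVs by dose, the plots mark cohorts and overlay individual values, and SAP 6.2 also plans concentration–time plots by participant. None of these yields a slope or an interval.

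A reader might also infer that the gap weakens dose escalation. It does not. Escalation rests on preliminary PK reviewed after each period (Protocol 6.6 and 6.6.1, SAP 7.1), whereas SAP 6.2 outputs belong to the final analysis.

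Comparing ×/÷1.61 with ±0.0355 is not like for like. One is a single contrast of 12 values; the other fits a straight line to 42. At 40%/25%, ordinary regression ignoring participants would give a slope whose actual uncertainty is about ±0.045, so much of the gain comes from assuming log-linearity and a smaller part from pairing. A gross departure would show in the plots anyway: a slope of 1.2 implies 300^0.2 = 3.13-fold drift. The model's benefit lies in moderate departures, and in attaching an interval to them.

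**Conclusion.** The point holds as a modest improvement. The plan sets out to understand how exposure depends on dose, yet provides no estimate with uncertainty, and the displays named for the purpose do not use the pairing that the crossover provides. The clause allowing further PK analyses does not close the gap: it specifies nothing and lets results stay out of the report.

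The size rests on assumed CVs and an assumed dose-to-cohort map. That neighbouring doses fall in different people is an inference from the interleaving text; the figure is not shown and doses may change. On those assumptions the slope is known to about ±0.03 to ±0.07 without a formulation term. With one, it is about ±0.05 to ±0.08 at 40%/25% and ±0.06 to ±0.095 at 50%/30%, and wider if within-participant variability is larger. It would be wrong to expect a narrow interval that settles proportionality: over 300-fold, 0.80–1.25 would usually be out of reach. It would also be wrong to fit the model across formulations without a term for them, because that can report non-proportionality where there is none.

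**What to change.** Add to SAP 6.2, for the final analysis, a descriptive mixed-effects power model:

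- ln(AUCinf) (as data permit), ln(AUClast) and ln(Cmax) regressed on ln(dose), with participant as a random effect.
- Fasted dose-escalation periods only.
- Formulation as a fixed term, or restriction to one formulation, with the choice stated in advance.
- Slope with 90% confidence interval, and a curvature check by a quadratic ln(dose) term or a residual plot.
- No pass/fail rule, in keeping with the absence of hypothesis testing.

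Keep the box plots and Table 5. The PROC MIXED code in SAP Appendix 1 needs only small changes, and no new data are collected. The cost is one more model per parameter, a log-linear assumption that must be checked, and a wider interval once formulation is handled. The result would inform the final dose–exposure conclusion and later dose choice; the in-study escalation projections are unaffected.

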9.3.3. Tertiary/Exploratory Endpoint(s) Analysis

The analysis of tertiary/exploratory endpoints will be detailed in the SAP.

9.3.4. Other Analyses

PGx or biomarker data from Retained Research Samples may be collected during or after the trial and retained for future analyses; the results of such analyses are not planned to be included in the CSR.

9.4. Interim Analyses

No interim analysis will be conducted for this study.

9.5. Sample Size Determination

A sample size of approximately 24 healthy adult participants (up to 3 cohorts of approximately 8 participants each) has been chosen based on the need to minimize first exposure to humans of a new chemical entity and the requirement to provide adequate safety, tolerability, and PK assessment at each dose level. At each dose level, approximately 6 participants are planned to receive PF-07853578 and approximately 2 participants are planned to receive placebo with all participants at the end of the study having received up to 4 doses of PF-07853578 and up to 2 doses of placebo.

10. SUPPORTING DOCUMENTATION AND OPERATIONAL CONSIDERATIONS

10.1. Appendix 1: Regulatory, Ethical, and Study Oversight Considerations

10.1.1. Regulatory and Ethical Considerations

This study will be conducted in accordance with the protocol and with the following:

- Consensus ethical principles derived from international guidelines, including the Declaration of Helsinki and CIOMS International Ethical Guidelines;
- Applicable ICH GCP guidelines;
- Applicable laws and regulations, including applicable privacy laws.

The protocol, protocol amendments, ICD, SRSD(s), and other relevant documents (eg, advertisements) must be reviewed and approved by the sponsor, submitted to an IRB/EC by the investigator, and reviewed and approved by the IRB/EC before the study is initiated.

Any amendments to the protocol will require IRB/EC approval before implementation of changes made to the study design, except for changes necessary to eliminate an immediate hazard to study participants.

Protocols and any substantial amendments to the protocol will require health authority approval prior to initiation except for changes necessary to eliminate an immediate hazard to study participants.

The investigator will be responsible for the following:

- Providing written summaries of the status of the study to the IRB/EC annually or more frequently in accordance with the requirements, policies, and procedures established by the IRB/EC;
- Notifying the IRB/EC of SAEs or other significant safety findings as required by IRB/EC procedures;
- Providing oversight of the conduct of the study at the site and adherence to requirements of 21 CFR, ICH GCP guidelines, the IRB/EC, European regulation 536/2014 for clinical studies, European Medical Device Regulation 2017/745 for clinical device research, and all other applicable local regulations.

10.1.1.1. Reporting of Safety Issues and Serious Breaches of the Protocol or ICH GCP

In the event of any prohibition or restriction imposed (ie, clinical hold) by an applicable regulatory authority in any area of the world, or if the investigator is aware of any new information that might influence the evaluation of the benefits and risks of the study intervention, Pfizer should be informed immediately.

In addition, the investigator will inform Pfizer immediately of any urgent safety measures taken by the investigator to protect the study participants against any immediate hazard, and of any serious breaches of this protocol or of the ICH GCP guidelines that the investigator becomes aware of.

10.1.2. Financial Disclosure

Not applicable.

10.1.3. Informed Consent Process

The investigator or the investigator's representative will explain the nature of the study, including the risks and benefits, to the participant and answer all questions regarding the study. The participant should be given sufficient time and opportunity to ask questions and to decide whether or not to participate in the trial.

Participants must be informed that their participation is voluntary. Participants will be required to sign a statement of informed consent that meets the requirements of 21 CFR 50, local regulations, ICH guidelines, privacy and data protection requirements, where applicable, and the IRB/EC or study center.

The investigator must ensure that each participant is fully informed about the nature and objectives of the study, the sharing of data related to the study, and possible risks associated with participation, including the risks associated with the processing of the participant's personal data.

The participant must be informed that their personal study-related data will be used by the sponsor in accordance with local data protection law. The level of disclosure must also be explained to the participant.

The participant must be informed that their medical records may be examined by Clinical Quality Assurance auditors or other authorized personnel appointed by the sponsor, by appropriate IRB/EC members, and by inspectors from regulatory authorities.

The investigator further must ensure that each study participant is fully informed about their right to access and correct their personal data and to withdraw consent for the processing of their personal data.

The medical record must include a statement that written informed consent was obtained before the participant was enrolled in the study and the date on which the written consent was obtained. The authorized person obtaining the informed consent must also sign the ICD.

Participants must be reconsented to the most current version of the IRB/EC-approved ICD(s) during their participation in the study as required per local regulations.

A copy of the ICD(s) must be provided to the participant.

Participants who are rescreened are required to sign a new ICD.

